12. DATA REPORTING / REGULATORY REQUIREMENTS

Adverse event lists, guidelines, and instructions for AE reporting can be found in Section 7.0 (Adverse Events: List and Reporting Requirements).

12.1. Data Reporting

12.1.1. Method

The Office of Data Quality (ODQ) will collect, manage, and perform quality checks on the data for this study.

12.1.2. Responsibility for Data Submission

Investigative sites within DF/HCC or DF/PCC are responsible for submitting data and/or data forms to the Office of Data Quality (ODQ) in accordance with DF/HCC policies.

12.2. Data Safety Monitoring

The DF/HCC Data and Safety Monitoring Committee (DSMC) will review and monitor toxicity and accrual data from this study. The committee is composed of medical oncologists, research nurses, pharmacists and biostatisticians with direct experience in cancer clinical research. Information that raises any questions about participant safety will be addressed with the Overall PI and study team.

The DSMC will review each protocol up to four times a year with the frequency determined by the outcome of previous reviews. Information to be provided to the committee may include: up-to-date participant accrual; current dose level information; DLT information; all grade 2 or higher unexpected adverse events that have been reported; summary of all deaths occurring within 30 days of intervention for Phase I or II protocols; for gene therapy protocols, summary of all deaths while being treated and during active follow-up; any response information; audit results, and a summary provided by the study team. Other information (e.g. scans, laboratory values) will be provided upon request.

12.3. Collaborative Agreements Language

N/A

13. STATISTICAL CONSIDERATIONS

Patients with MDS progressing after or unlikely to respond to front-line therapeutic options have limited salvage treatment options. This study seeks to determine whether MBG453 has activity in this setting.

The primary outcome will be the overall response rate within the first 6 months of treatment, which will be a composite endpoint of complete remission (CR), partial remission (PR), hematologic improvement (HI), transfusion independence (TI), and complete remission with incomplete hematologic recovery (CRh). We will assume that the null response rate is 0.15 based on prior studies (Fenaux et al., 2020; Garcia-Manero et al., 2020; Giagounidis et al., 2014; Oliva et al., 2017; Santini et al., 2016). Although patients may have received HMA prior to enrollment, we will plan to analyze the post-HMA group as a distinct subgroup. Secondary outcomes include adverse event monitoring, duration of response, number of patients receiving MBG453 and duration of treatment, overall survival, progression-free survival, and toxicities. Descriptive statistics will be used for patient and treatment characteristics and for correlative studies. We will estimate OS, PFS, and duration of response using the method of Kaplan and Meier. Toxicities will be presented using descriptive statistics, evaluated according to the NCI criteria, and summarized by patient as well as by type and grade.

13.1. Study Design/Endpoints

The primary objective is to evaluate the ORR of MBG453 in lower-risk MDS after standard front-line therapy. The ORR will be comprised of CR, PR, HI, TI, and CRh, as described in section 11.1. We will assess response as the best overall response within the first 6 months of treatment.

Secondary endpoints include:

- The rates and severity of adverse events associated with MBG453 in lower risk MDS
- The rates of 1-year overall survival (OS), progression free survival (PFS), time to disease progression, and duration of response to therapy with MBG453.
- Response to therapy according to pretreatment disease and patient characteristics, monitoring disease-specific molecular, immunophenotypic, and cytogenetic evolution during treatment (exploratory analysis)
- Changes in cell surface marker expression, Immune cell subsets, and molecular clonal evolution during treatment and at the time of progression (exploratory analysis)

This study will follow a Simon's Optimal Two-Stage Phase II design. The null hypothesis that the true response rate is $P=0.15$ will be tested against a one-sided alternative. In the first stage, 10 patients will be accrued. If there are no more than 1 responses in these 10 patients, the study will be stopped. Otherwise, 12 additional patients will be accrued for a total of 22. The null hypothesis will be rejected if 6 or more responses are observed in 22 patients. This design yields a type I error rate of 0.09 and power of 0.80 when the true response rate is 0.35.

In order to closely monitor for signals of toxicity in the lower-risk MDS cohort, we will assess

the first six patients who are enrolled for dose limiting toxicities (DLTs) during the first 28 days of treatment. If more than 1 of the first 6 patients experiences a DLT the study enrollment will stop and reviewed for safety prior to further enrollment. The following table provides the probability that no more than 1 in 6 patients experiences a DLT and the study proceeds without interruption, given the true but unknown rate of DLT:

	True but unknown probability of experiencing a DLT				
	0.10	0.20	0.30	0.40	0.50
Pr(success)	0.89	0.66	0.42	0.23	0.11

Follow-up will be planned 1 year after end of treatment or death, whichever occurs first. The toxicities will be measured according to NCI-CTC version 5.0 (<http://ctep.info.nih.gov>), and tabulated according to the stage of dose escalation.

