5.3. Agent Administration

5.3.1. MBG453

MBG453 100 mg/1 mL and 400 mg/4 mL Liquid in vial. MBG453 100 mg/1 mL Concentrate for solution for infusion is used for intravenous administration from a dose of 12 mg up to a maximal dose of 2400 mg.

Administration:

MBG453 is administered as an intravenous infusion given over 30 minutes, but which may be given over up to 2 hours, if clinically indicated. The maximum administration time is 120 min \pm 10 min.

Shorter infusion times can be applied, since longer infusion times are considered worst-case with regards to potential protein adsorption. The selection of infusion speed within that requirement is in the responsibility of the project-responsible clinician and needs to comply with the specifications given by the infusion pump.

When administration is complete, flush the line with at least 25 mL of 5% dextrose solution to guarantee that all the MBG453 solution for infusion remaining in the infusion line has been administered.

Dosing:

MBG453 will be administered at a dose of 800mg on day 1 of a 28-day cycle.

Drug, Tubing and Filtration:

Only the materials (infusion bags, infusion syringes, infusion lines and in-line filter) specified below should be used for administration of the study medication. The solution for infusion must be infused through a 0.2 micron in-line filter. The infusion sets including the intravenous filter set have to be prepared according to the instructions supplied by the manufacturers.

The infusion set materials listed below are compatible with MBG453. The following materials are accepted to be used in clinical trials for administration of MBG453 Solution for infusion prepared in 5 % dextrose solution (100 mL bags).

Compatible materials of infusion sets components (doses from 40mg to 2400):

- *100 mL 5% Dextrose infusion bag materials in contact with the drug product:* PolyVinyl Chloride (all plasticizers); PolyEthylene
- *Infusion line materials, material in contact with the drug product (maximum length: 300 cm):* PolyVinyl Chloride (all plasticizers); PolyEthylene
- *Infusion filter materials membrane type:* Positively charged Polyamide, Positively charged PolyEtherSulfone, Neutral PolyEtherSulfone

The infusion set (bag, line, and filter) selected for the study should be approved according to local regulation.

Special Equipment:

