6. DOSING DELAYS/DOSE MODIFICATIONS

MBG453 may be delayed due to toxicities. Doses may be delayed for up to 28 days for toxicity; toxicities that result in more than 28 days delay should result in discontinuation from the study medication. Patients that are deriving clinical benefit but require a treatment delay beyond 28 days for non-toxicity events should be discussed with the principal investigator.

Dosing may be resumed once an AE has resolved to baseline or to Grade 1. If a treating investigator considers it in the patient's best interest to resume therapy before resolution of an AE or to resume without dose modification this may be considered on a case-by-case basis after discussion with the overall PI of the trial.

Dose modifications of MBG453 may be accomplished through dose reduction or altering the treatment interval; provisional dose levels are shown below.

Dose delays and modifications will be made as indicated in the following table(s). The descriptions and grading scales found in the revised NCI Common Terminology Criteria for Adverse Events (CTCAE) version 5.0 will be utilized for dose delays and dose modifications. A copy of the CTCAE version 5.0 can be downloaded from the CTEP website

http://ctep.cancer.gov/protocolDevelopment/electronic_applications/ctc.htm.

Dose Level	Dose
-2	240 mg every 28 days
-1	400 mg every 28 days
0	800 mg every 28 days

If the patient experiences an AE meeting the criteria for DLT as outlined in section 5.4, including events outside the DLT period, treatment should be held. Patients may resume treatment after resolution to Grade 1 or to the patient's baseline value. If this event occurs during the first cycle (whether or not they are among the first 6 patients being evaluated for DLT assessment) a dose modification must be made. If this event occurs after the first cycle the patient may resume at the same or a lower dose at the discretion of the investigator. Specific guidance is provided below.

Infusion Reaction	Management/Next Dose for MBG453
≤ Grade 1	Decrease infusion rate until recovery
Grade 2	Stop Infusion. Before restarting, pre-medicate according to local institutional guidelines. Restart infusion at 50% of previous rate under continuous observation. Ensure that there is a minimum observation period of 1 hour prior to restarting the infusion(s). If the AE recurs at the reinitiated slow rate of infusion, and despite oral pre-medication, then discontinue treatment
Grade 3	Discontinue treatment

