7.3.5. Protocol-Specific Adverse Event Reporting Exclusions

For this protocol only, the AEs/grades listed below do not require expedited reporting to the Overall PI or the DFCI IRB. However, they still must be reported through the routine reporting mechanism (i.e. case report form). Grade 1-2 hematologic toxicities do not need to be reported as AEs unless felt clinically relevant.

- Hematologic toxicity of any grade does not need expedited reporting unless felt to meet criteria in Section 5.4 and be related to MBG453.
- Electrolyte abnormalities (K, Na, HCO₃, Chloride, Phosphorus, Magnesium) that are not felt to be clinically significant and/or improve to grade < 3 within 72 hours.

Events not considered to be SAEs are hospitalizations for:

- A standard procedure for protocol therapy administration. However, hospitalization or prolonged hospitalization for a complication of therapy administration will be reported as an SAE.
- Routine treatment or monitoring of the studied indication not associated with any deterioration in condition
- The administration of blood or platelet transfusion as routine treatment of studied Indication. However, hospitalization or prolonged hospitalization for a complication of such transfusion remains a reportable SAE.
- A procedure for protocol/disease-related investigations (e.g., surgery, scans, endoscopy, sampling for laboratory tests, bone marrow sampling). However, hospitalization or prolonged hospitalization for a complication of such procedures remains a reportable SAE.
- Hospitalization or prolongation of hospitalization for technical, practical, or social reasons, in absence of an AE.

- A procedure that is planned (i.e., planned prior to starting of treatment on study); must be documented in the source document and the CRF. Hospitalization or prolonged hospitalization for a complication remains a reportable SAE.
- An elective treatment of or an elective procedure for a pre-existing condition unrelated to the studied indication.
- Emergency outpatient treatment or observation that does not result in admission, unless fulfilling other seriousness criteria above.

If an AE is considered serious, both the AE Case Report Form and the SAE Report Form must be completed. For each SAE, the Investigator will provide information on severity, start and stop dates, relationship to study drugs, action taken regarding study drugs, and outcome.

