7.6. Routine Adverse Event Reporting

All Adverse Events **must** be reported in routine study data submissions to the Overall PI on the toxicity case report forms. **AEs reported through expedited processes (e.g., reported to the IRB, FDA, etc.) must also be reported in routine study data submissions.**

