13.6. Analysis of Secondary Endpoints

Secondary endpoints include the rates and severity of adverse events, 1-year overall survival (OS), progression free survival (PFS), time to disease progression, and duration of response to therapy with MBG453. Descriptive statistics will be used for patient and treatment characteristics and for correlative studies. We will estimate OS, PFS, and duration of response using the method of Kaplan and Meier. Toxicities will be presented using descriptive statistics and evaluated according to the NCI criteria.

Planned exploratory correlative studies will seek to characterize changes in immune and myeloid populations during treatment with MBG453, as well as any associations between mutation profiles and patient responses. These will be analyzed using descriptive statistics.

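### Section 13.1 tabulates toxicity by a dose-escalation stage that this trial does not have, and none of the adverse-event analysis text ties hematologic grades to baseline

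*Combined protocol and SAP*

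**What the plan says.** The safety endpoint heads the list of secondary endpoints in section 13.1: "The rates and severity of adverse events associated with MBG453 in lower risk MDS". Three places say how it will be analyzed.

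- Section 13.1: toxicities are graded by NCI criteria and "tabulated according to the stage of dose escalation".
- Section 13 (opening text): toxicities are descriptive and "summarized by patient as well as by type and grade".
- Section 13.6: "Toxicities will be presented using descriptive statistics and evaluated according to the NCI criteria".

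Section 13.7.1 adds only that participants are evaluable for treatment-related toxicity from the first dose.

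On dosing, section 5.3.1 says: "MBG453 will be administered at a dose of 800mg on day 1 of a 28-day cycle". Section 6 says: "Dose modifications of MBG453 may be accomplished through dose reduction or altering the treatment interval". It lists level 0 (800 mg) and two lower levels (400 mg and 240 mg), all every 28 days.

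On the population, section 3.1.1 lists platelets below 50k/uL and ANC below 500/uL among the qualifying categories, for patients the treating physician considers to need treatment.

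**The concern.** There are two separate defects.

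The first is a stated analysis rule that does not fit the design. A table by escalation stage needs at least two stages, and this trial has none. The same document gives a different rule in section 13, so the programmer has two instructions and one of them is void.

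The second matters more. Some patients qualify because they already have a severe cytopenia. None of the analysis text says whether an entry cytopenia still present at the first on-treatment blood count is an adverse event, or whether only worsening counts. With no control arm, the reader has no outside reference for how much hematologic toxicity is disease. The answer would rest on each investigator's attribution.

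Hematologic toxicity is also a plausible signal for this drug. Section 2.2 lists ten possibly related grade 3 or higher events in 26 earlier single-agent patients with MDS or AML. Thrombocytopenia (4) and neutropenia (2) make up 6 of those 10.

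**Working it through.** **1. Is there an escalation stage?** Every patient starts at 800 mg (5.3.1). The first six form a safety lead-in at that same dose (5.4, 13.1). The 400 mg and 240 mg levels are reached only by reduction within a patient (6). The number of escalation strata is one, so the section 13.1 table collapses to the overall table.

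**2. Where does baseline appear?**

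| Section | Purpose | Reference to baseline |
|---|---|---|
| 13, 13.1, 13.6, 13.7.1 | AE analysis | None |
| 5.4 | DLT classification | Refers to new grade 4 cytopenias and to the baseline of a given cell line |
| 6, hematologic table | Dosing | Names baseline only where it was grade 2 |
| 7.3.2 | AE reporting | Counts events after the first dose; silent on persisting entry cytopenia |
| 10, calendar footnote h | Laboratory baseline | Sets baseline at cycle 1 day 1, in a note mainly about chemistry and INR |

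The protocol recognizes the issue for DLTs and, in part, for dosing. It does not carry it into the AE analysis.

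**3. Are the data there?** Yes. The calendar schedules blood counts, with database timepoints, at:
- screening;
- days 1, 8, 15 and 22 of cycles 1 and 2;
- days 1 and 15 of cycles 3 and 4;
- day 1 of each later cycle, and end of treatment.

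**4. The plan's own safety figure.** Section 13.1 gives the probability of at most one DLT in six. The formula is (1−p)^6 + 6p(1−p)^5.
- p = 0.10: 0.8857 (stated 0.89)
- p = 0.20: 0.6554 (stated 0.66)
- p = 0.30: 0.4202 (stated 0.42)
- p = 0.40: 0.2333 (stated 0.23)
- p = 0.50: 0.1094 (stated 0.11)

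All five reproduce. The lead-in has its own rules and is not touched by this point.

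**5. How much the convention could matter (illustration only).** Let f be the share of 22 patients already at grade 3 or higher on entry, and q the rate of new grade 3 or higher cytopenia in the rest. The documents give neither, nor do they give CTCAE cut-offs, so all of these are assumptions. If every on-study grade is counted, the rate is f + (1−f)q. If only new events are counted, the number is 22(1−f)q. With q = 0.10:

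| f | Rate, every on-study grade | Patients of 22 | New events only |
|---|---|---|---|
| 0 | 10% | 2.20 | 2.20 |
| 0.25 | 32.5% | 7.15 | 1.65 |
| 0.50 | 55% | 12.10 | 1.10 |
| 0.75 | 77.5% | 17.05 | 0.55 |

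The last two columns are the two conventions. The plan does not say which applies. Under the second, the inflation disappears.

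**6. A limit of any shift count.** A patient who enters at the top laboratory grade cannot move up. Counting grade worsening over all 22 would put patients in the denominator who can never enter the numerator.

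**The case against.** The strongest reply is that little is lost. Section 13 gives a summary that can be carried out, and with one starting dose the section 13.1 phrase is probably leftover wording. The analysis text is silent on baseline; it does not say that entry cytopenias count as toxicity. Reportable events are those after the first dose (7.3.2), evaluability is for treatment-related toxicity (13.7.1), and each event carries a five-level attribution (7.2). All of this stands, and it rules out three stronger readings.

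- A reader might infer that the hematologic safety results cannot be read at all. The documents do not support that: a usable summary, attribution and serial counts all exist. What is missing is a prespecified rule and display.
- A reader might pick 5 to 15 patients with severe entry cytopenia and conclude that 5/22 = 23% to 15/22 = 68% would show severe toxicity with no drug effect. Those counts are not in the documents. The conclusion also needs every entry cytopenia to be logged as an on-study event, which sits poorly with 7.3.2 and 13.7.1.
- A reader might infer that the whole hematologic numerator depends on the site. Section 7.6 says all adverse events must "be reported in routine study data submissions to the Overall PI on the toxicity case report forms", while section 7.3.5 says: "Grade 1-2 hematologic toxicities do not need to be reported as AEs unless felt clinically relevant". But 7.3.5 is worded as a protocol-specific exception and reads as the narrower rule. It waives AE recording for grades 1 and 2 only; grade 3 and higher events are still recorded.

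The reply does not answer two points. Counting after the first dose does not settle whether a persisting entry cytopenia is an event. And a shift table that could be built later is not a planned one.

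**Conclusion.** The point holds in a limited form. The tabulation axis in section 13.1 is void for this design and disagrees with section 13. Separately, no AE analysis text refers to baseline grade in a population that can qualify by severe cytopenia, so hematologic AE rates by grade alone would be hard to interpret and would depend on attribution.

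No size can be given from the documents: they state neither the baseline mix nor the counting convention. The table above shows only that the choice of convention could matter, under assumed values of f and q.

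The point affects the hematologic part of one descriptive secondary endpoint. Non-hematologic and immune-related events, the DLT lead-in and the response-rate test are unaffected. It should be corrected before the analysis, because a stated rule is wrong and a better method is available from data already planned.

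**What to change.** 1. In section 13.1, delete the escalation phrase. State one rule, consistent with section 13: worst grade per patient, by type and attribution, over all treated patients.
2. For neutrophils, platelets and hemoglobin, define treatment-emergent hematologic toxicity as worsening from the cycle 1 day 1 value. State that the calendar's baseline definition applies to blood counts.
3. Add a baseline-to-worst-grade shift table for each of the three, derived from the scheduled blood counts. AE forms alone would miss most grade 1 and 2 changes because of 7.3.5.
4. Use as denominator the patients able to worsen in that cell line. For patients already at the top grade, report the change in count from baseline to nadir.

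A cross-reference from 7.6 to the 7.3.5 exception would be optional tidying. A split by dose level and cycle is not needed: with 22 patients the cells would be sparse, and section 6 also allows interval changes that dose level would not capture.

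The cost is a few lines of SAP wording and one programmed shift display with its nadir summary. No new assessments or site work are required.

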13.2. Sample Size, Accrual Rate and Study Duration

A maximum of 22 patients will be accrued on this study. We anticipate that these patients will be accrued over an 18 month period across centers, for a total study duration of 18 months of accrual, and up to 12 months of follow up for analysis. Reporting on the primary outcome would occur after all patients have been dosed for up to 6 months or come off treatment in that time period. Secondary outcomes would be reported approximately 30 months after study initiation.

Accrual Targets				
Ethnic Category	Sex/Gender			
	Females		Males	Total
Hispanic or Latino	1	+	2	= 3
Not Hispanic or Latino	7	+	12	= 19
Ethnic Category: Total of all subjects	(8)	+	(14)	= (22)
Racial Category				
American Indian or Alaskan Native	0	+	0	=
Asian	0	+	0	=
Black or African American	1	+	1	=
Native Hawaiian or other Pacific Islander	0	+	0	=
White	7	+	13	=
Racial Category: Total of all subjects	(8)	+	(14)	= (22)

